15.3. EXPLORATORY EFFICACY

15.3.1. EXPLORATORY EFFICACY ENDPOINTS AND DERIVATIONS

15.3.1.1. Acute Exacerbation of Chronic Sinusitis

The percentages of subjects reporting acute exacerbation of CS (AECS) at Weeks 4, 8, 12, 16, 20 and 24 are exploratory endpoints, where AECS will be assessed by the investigator. AECS is defined as a sudden worsening of symptoms in a subject resulting in the treating physician reporting an escalation of treatment. This will be reported by the investigator on the Follow-up eCRF.

15.3.1.2. Improvement from Baseline in Nasal Polyp Severity Within Middle Meatus

The percentage of subjects with improvement from baseline in nasal polyp severity within the middle meatus in CSwNP subjects at Week 24 will be analyzed. Investigators will evaluate the severity of nasal polyps in the middle meatus using endoscopy at the Week 24/EOT visit by grading polyp severity as “better,” “worse,” or “the same” in comparison to the Baseline severity evaluated at Day 1 before the insertion procedure. A subject will be considered to have an improvement from baseline if both sinuses are assessed to be “better” than baseline or one side is assessed to be “better” than baseline and the other side to be “the same” as baseline.

15.3.1.3. CFBL in Endpoints by Absence or Presence of Nasal Polyps

The secondary endpoints analysis will be repeated using the subgroups of subjects without nasal polyps (CSsNP), and subjects with nasal polyps (CSwNP). The endpoints to be summarized by these subgroups are:

- CFBL in CS7DA4S score at Weeks 1, 2, 3, 4, 8, 12, 16, 20 and 24

- CFBL in 7-day average score of individual cardinal CS symptoms at Weeks 1, 2, 3, 4, 8, 12, 16, 20 and 24
- CFBL in SNOT-22 domain and total scores at Weeks 2, 4, 8, 12, 16, 20 and 24
- CFBL in SF-36 domain and overall component summary measure scores at Week 24
- Percentage of subjects with at least 1-point decrease in any area for the bilateral Zinreich score at Week 24
- CFBL in each of the 5 bilateral Zinreich sinus scores, Zinreich OMC score and Zinreich total score at Week 24
- CFBL in USPIT™ total olfaction score at Week 24

15.3.1.4. CFBL in Endpoints at Post-Treatment Visits

The secondary endpoint analysis will be repeated for the post-treatment visits. The endpoints to be explored for these visits are:

- Proportion of subjects with improvement from baseline in nasal polyp severity within the middle meatus at Week 28
- CFBL in CS7DA4S total score at Weeks 28, 32, 36, 40, 44 and 48
- CFBL in 7-day average score of individual cardinal CS symptoms at Weeks 28, 32, 36, 40, 44 and 48
- CFBL in SNOT-22 domain and total scores at Weeks 28, 32, 36, 40, 44 and 48
- CFBL in SF-36 domain and overall component summary measure scores at Week 48
- CFBL in UPSIT at Week 28.

15.3.2. MISSING DATA IMPUTATION METHODS FOR EXPLORATORY EFFICACY ENDPOINTS

No missing data methods will be used for exploratory analysis.

15.3.3. ANALYSIS OF EXPLORATORY EFFICACY ENDPOINTS

The exploratory efficacy endpoints that are continuous will be compared between treatments at each post-baseline timepoint in the same manner as the primary efficacy analysis in Section 15.1.3 for the ITT analysis set. For the efficacy endpoints to be analyzed by CSsNP and CSwNP subgroups, the analysis will be a repeat of Section 15.1.3, however the model will not include the presence of nasal polyps as a fixed effect.

For dichotomous exploratory efficacy endpoints, treatments will be compared in the same manner as the proportion

of subjects with at least 1-point decrease from baseline in the Zinreich score in at least 1 pair of the anterior ethmoid, maxillary, posterior ethmoid, frontal or sphenoid sinuses key secondary endpoint in Section 15.2.4.2, replacing the baseline bilateral Zinreich score with the baseline CS7DA4S score. This analysis will be carried out for the ITT analysis set.

In addition, for all endpoints measured longitudinally at various visits during the study, a generalized estimating equation (GEE) linear regression and logistic regression will be used to compare treatments over time for continuous and dichotomous endpoints, respectively. The estimates, SE, 90% CIs and p-values will be presented for each visit. In the GEE, only treatment stage timepoints will be analyzed; assessments with only one follow-up timepoint will not be analyzed.

The assumed within-subject correlation matrix structure will be unstructured. If the unstructured model does not converge, then an autoregressive (1) structure will be assumed. Included as independent variables for each outcome endpoint will be treatment group, visit, treatment-by-visit, stratification variables, and the baseline value of the endpoint being analyzed. This will be carried out on ITT subjects with available data for the below endpoints:

- CFBL in CS7DA4S total score
- CFBL in 7-day average score of individual cardinal CS symptoms
- CFBL in SNOT-22 domain and total scores

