### **10.6.4 Exploratory Endpoint Analysis**

A one-sided 0.05 level of significance will be used to compare treatments for each exploratory efficacy endpoint at each visit; there will be no adjustment for multiple comparisons. These analyses will be performed in the ITT analysis set with available data and repeated using subjects in the PP analysis set. There will be no imputation of missing data for these analyses.

The exploratory efficacy endpoints that are continuous variables will be compared between treatments at each post-Baseline time point in the same manner as the primary endpoint. For dichotomous efficacy endpoints, treatments will be compared using logistic regression adjusting for baseline score and randomization strata.

As further exploratory analyses on all endpoints measured longitudinally at various visits during the study, generalized estimating equation (GEE) linear regression (for continuous outcomes) and GEE logistic regression (for dichotomous outcomes) will be used to compare treatments over time; the assumed within-subject correlation matrix structure will be unstructured; if the unstructured model does not converge, then an autoregressive (1) structure will be assumed. Included as independent variables for each outcome variable will be treatment group, visit, treatment-by-visit and the baseline value of the variable being analyzed. If the treatment-by-visit interaction is not significant at the 0.10 level of significance, it will be removed from the GEE model. This will be carried out on ITT subjects with available data.

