7.4. ADJUSTMENTS FOR COVARIATES AND FACTORS TO BE INCLUDED IN ANALYSES

The following covariates and factors will be used in the primary and secondary analyses when an analysis of

covariance (ANCOVA) is performed. For details of their inclusion in the models please refer to Section 15.

- Covariates:
 - Baseline value of the concerned endpoint
- Factors:
 - Treatment group (fixed effect)
 - Randomization stratification variables
 - Nasal allergy (Yes/No)
 - Nasal polyps (Yes/No)

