15.1.3. PRIMARY ANALYSIS OF PRIMARY EFFICACY ENDPOINT

The CFBL for CS7DA4S at Week 4 will be analyzed using the ITT analysis set. The following analysis will be performed for the CFBL CS7DA4S score at Week 4:

- Summary statistics for the Baseline CS7DA4S score, the Week 4 CS7DA4S score and the CFBL at Week 4
- An ANCOVA model for CFBL at Week 4. The ANCOVA model will include the baseline CS7DA4S score as a covariate, treatment group and the randomization stratification variables (nasal allergy, nasal polyps) as fixed effects.

Each hypothesis as described in Section 7.8 will be tested at a one sided 0.05 alpha level of significance by the ANCOVA model. The LS means and SE of each treatment group, the LS mean difference of each LYR-210 procedure against the Sham procedure and their SEs, 90% CIs, and p-values estimated by the model will also be provided.

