15.2.4. ANALYSIS OF KEY AND OTHER SECONDARY EFFICACY ENDPOINTS

15.2.4.1. Analysis of CFBL in CS7DA4S Individual and Total Scores at Weeks 8, 12, 16, 20 and 24

The analysis of the CFBL in CS7DAS total score will be conducted using an ANCOVA model as per Section 15.1.3. Week 24 is considered a key secondary endpoint, while Weeks 8, 12, 16, and 20 are considered as non-key secondary endpoints and all other visits as exploratory endpoints.

Additionally, the 7-day average score of nasal blockage/obstruction/congestion, reduction/loss of sense of smell, facial pain/pressure and anterior/posterior nasal discharge at Weeks 1, 2, 3, 4, 8, 12, 16, 20, 24 will be analyzed as per Section 15.1.3.

This analysis will be repeated for the ITT and PP analysis sets.

The same three sensitivity and supportive subgroup analyses as for the primary endpoint as detailed in Sections 15.1.4 and 15.1.5.2 will be repeated for the CS7DA4S total scores at all Weeks. Furthermore, the analysis of the CS7DA4S total score at all Weeks by CSsNP and CSwNP subgroups will be repeated with missing data imputed as per Section 15.1.2.

For all other endpoints, the sensitivity analyses based on the PP analysis set and based on the ITT analysis set but with missing data imputed based on LOCF will be performed. That is, no sensitivity analysis based on the ITT analysis set with missing data imputed based on the multiple imputation method will be performed for the other secondary efficacy endpoints.

Additionally, a plot of the LS means and SE for CFBL for CS7DA4S total and individual symptom scores at each timepoint up to Week 24 and Week 48 will be provided for the primary and final data analysis, respectively.

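### The SAP gives two different baseline covariates for the individual-symptom endpoints and for the polyp-subgroup analyses; the literal reading of Section 15 costs precision and should be settled in the text

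*SAP*

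**What the plan says.** **Text leading to baseline CS7DA4S.**
- SAP 15.1.3 (primary analysis): "The ANCOVA model will include the baseline CS7DA4S score as a covariate".
- SAP 15.2.4.1: the 7-day averages of the four individual symptoms, at nine visits from Week 1 to Week 24, "will be analyzed as per Section 15.1.3". No substitution of the covariate is stated.
- SAP 15.3.3, continuous endpoints by polyp subgroup: "the analysis will be a repeat of Section 15.1.3, however the model will not include the presence of nasal polyps as a fixed effect". Dropping the polyp factor is the only change named.
- SAP 15.3.3, dichotomous exploratory endpoints: the logistic model of 15.2.4.2, "replacing the baseline bilateral Zinreich score with the baseline CS7DA4S score". SAP 15.3.1.3 lists among the exploratory endpoints "Percentage of subjects with at least 1-point decrease in any area for the bilateral Zinreich score at Week 24".

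**Text leading to the endpoint's own baseline.**
- SAP 7.4 gives the covariate for primary and secondary ANCOVAs as "Baseline value of the concerned endpoint", but refers to Section 15 for how it enters the models.
- SAP 15.3.1.3: "The secondary endpoints analysis will be repeated using the subgroups of subjects without nasal polyps (CSsNP), and subjects with nasal polyps (CSwNP". For the Zinreich responder, the secondary analysis is the model in 15.2.4.2, which adjusts for baseline total bilateral Zinreich score.
- The GEE paragraph of SAP 15.3.3, which covers the individual symptoms, adjusts for the baseline of the endpoint analysed.
- SAP 15.2.4.2, 15.2.4.5 and 15.2.4.6 write out the substitution for Zinreich change, SNOT-22 and SF-36v2, and UPSIT.

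**Protocol.** For dichotomous exploratory endpoints, Section 10.6.4 says "treatments will be compared using logistic regression adjusting for baseline score and randomization strata", without naming the score. SAP 3.3 lists no change from the protocol on this point.

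**The concern.** A change score is usually best predicted by its own baseline, and adjusting for it also deals with chance baseline differences between arms. A programmer who follows 15.2.4.1 and 15.3.3 to the letter would adjust each symptom for the four-symptom composite, and an MRI response for a symptom score. The substitution is written out for every other instrument in 15.2.4, so its absence for the symptoms looks like an oversight. The by-visit ANCOVA and the GEE would then adjust the same symptom score for different baselines.

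Two things are at stake. One is precision, in a trial with about 21 evaluable subjects per arm and still fewer per polyp subgroup. The other is pre-specification: where two models can each be justified from the SAP, the choice between them stays open after results are seen.

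**Working it through.** **1. The rules side by side.**

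| Endpoint | Route to baseline CS7DA4S | Route to own baseline |
|---|---|---|
| Four individual symptoms | 15.2.4.1 to 15.1.3 | 7.4; GEE in 15.3.3 |
| Zinreich responder by polyp subgroup | 15.3.3, dichotomous rule | 15.3.1.3 to 15.2.4.2 |
| SNOT-22, SF-36v2, UPSIT, Zinreich change by polyp subgroup | 15.3.3, repeat of 15.1.3 | 15.3.1.3 to 15.2.4.5, 15.2.4.6, 15.2.4.2 |

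Section 7.4 cannot settle the first row, because it defers to Section 15. It does not reach the second row at all, because it is limited to ANCOVAs of primary and secondary endpoints.

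**2. The plan's own figure.** The documents give no figure for the covariate choice. The 73% power in SAP 7.1 serves only as a benchmark. With 21 per arm, difference 1.7, SD 2.4 and one-sided 0.05, the standard error is 2.4 × √(2/21) = 0.741 and 1.7/0.741 = 2.295. Power is 74.2% by the normal approximation and 73.0% by the noncentral t with 40 df. The stated figure reproduces as the power of one dose-versus-sham comparison.

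**3. Individual symptoms (linear model).** Let r be a symptom's baseline-to-follow-up correlation and c the baseline correlation between symptom and composite. Both are assumptions. Take unit variance at both times, and assume that the composite adds nothing to the prediction once the symptom's own baseline is known. The residual variance of the change is then:
- own baseline: 1 − r²
- composite baseline: 2(1 − r) − [c(1 − r)]²

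| r | Own | Composite, c = 0.5 | SE ratio | Composite, c = 0.7 | SE ratio |
|---|---|---|---|---|---|
| 0.3 | 0.9100 | 1.2775 | 1.185 | 1.1599 | 1.129 |
| 0.5 | 0.7500 | 0.9375 | 1.118 | 0.8775 | 1.082 |
| 0.7 | 0.5100 | 0.5775 | 1.064 | 0.5559 | 1.044 |

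The standard error is 4% to 18% larger. The variance ratio runs from 1.09 to 1.404, so 63 subjects carry the information of 63/1.09 = 58 down to 63/1.404 = 45.

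A wider grid with between-symptom correlation 0 to 0.6 gives SE ratios of 1.03 to 1.19. A comparison with 73% power under its own baseline would have 60% to 71% under the composite.

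The three-arm ANCOVA was also simulated, with 21 per arm, entry composite of at least 7, both strata in the model and a true effect of −0.40. The mean estimate was −0.40 under either covariate in all six settings, and the SE ratio was 1.035 to 1.159. The covariate changes the spread of the estimate, not its centre.

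**4. Zinreich responder (logistic model).** Assumptions: 40% responders under sham; an odds ratio of 3 or 5 conditional on baseline Zinreich; baseline Zinreich replaced by a covariate correlated 0 to 0.5 with it; large-sample fits (n = 400,000).

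| Log-odds per SD of baseline Zinreich | Fitted OR when conditional OR is 3 | Fitted OR when conditional OR is 5 |
|---|---|---|
| 0.5 | 2.8-2.9 | 4.6-4.7 |
| 1.0 | 2.5-2.6 | 3.8-4.0 |
| 1.5 | 2.2-2.3 | 3.1-3.5 |

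The log-odds ratio is about 4% to 30% smaller. This is non-collapsibility: the two models estimate different conditional odds ratios.

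**The case against.** The strongest defence is that the SAP already intends own baselines. Section 7.4 says so, the GEE uses them for the same symptom scores, and 15.2.4.1 treats individual and total scores under one heading, so a reference to 15.1.3 could mean the matching baseline. For the MRI responder, 15.3.1.3 is the more specific rule. Baseline CS7DA4S also has a protocol precedent: Section 10.6.3 names it in the logistic model for dichotomous endpoints outside the key secondaries. It is a sensible covariate for acute exacerbation (AECS) and for polyp better/same/worse, which have no numeric baseline of their own. All of this stands. It shows that the SAP conflicts with itself, not that it plainly prescribes the wrong covariate; it does not remove the conflict.

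A reader might infer that the symptom effects would be attenuated or biased. The documents and the check do not support that: in a randomized linear ANCOVA either covariate gives the same expected difference. If one symptom happened to be imbalanced by 0.3 SD with a balanced composite, the estimate would be off by 0.3 × (1 − r), that is 0.09 to 0.21 SD for r = 0.7 to 0.3. But this averages to zero over randomizations and is already reflected in the larger standard error, so it is not a second harm.

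A reader might also take the odds-ratio shift as bias. It is a change of target. The standard error of the log-odds ratio does not generally grow when the prognostic covariate is dropped, so the shrinkage alone overstates the loss of power.

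**Conclusion.** The point holds as an internal conflict in the SAP, with a modest cost if the literal reading is followed. For the four individual-symptom endpoints the standard error would be about 4% to 18% larger, conditional on the assumed correlations (0.3-0.7 from baseline to follow-up, 0.5-0.7 with the composite). For the polyp-subgroup Zinreich responder the model would target an odds ratio nearer 1, with some loss of power; the size depends on how strongly baseline Zinreich predicts response, which the documents do not say. The loss for subgroup SNOT-22, SF-36v2, UPSIT and Zinreich change was not quantified.

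The reach is limited. The primary endpoint and the ITT key secondary MRI model are unaffected. The endpoints concerned are secondary or exploratory, p-values are nominal under SAP 7.8, and SAP 7.6 drops inference for a subgroup in which any arm has fewer than 5 subjects. It is still worth correcting, because it removes a free choice of model.

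**What to change.** - **SAP 15.2.4.1:** state that, for each individual symptom, baseline CS7DA4S in the 15.1.3 model is replaced by the baseline 7-day average of the symptom analysed.
- **SAP 15.3.3, continuous endpoints:** state that every exploratory or subgroup model uses the endpoint's own baseline. This covers SNOT-22, SF-36v2, UPSIT and Zinreich change by polyp group, which correcting only the dichotomous rule would miss.
- **SAP 15.3.3, dichotomous endpoints:** state that the Zinreich responder by polyp group keeps baseline total bilateral Zinreich score, and that baseline CS7DA4S is used only where there is no numeric own baseline (AECS, polyp better/same/worse).

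The cost is a few sentences in two SAP sections, to be settled before unblinding. All the baselines are already collected.

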16. SAFETY OUTCOMES

All outputs for safety outcomes will be based on the SAF.

There will be no statistical comparisons between the treatment groups for safety data, unless otherwise specified with the relevant section.

16.1. ADVERSE EVENTS

AEs will be coded using MedDRA version 23.0 or later.

- Prior AEs are defined as any AE starting before the bilateral insertion/Sham procedure.
- Treatment emergent adverse events (TEAEs) are defined as any AE starting or worsening on or after the bilateral insertion/Sham procedure, but before or on 28 days after the removal/Sham procedure.
- Post-treatment AEs are defined as any AE starting or worsening more than 28 days after the removal/Sham procedure.

See [APPENDIX 2](#) for the handling of partial dates for AEs. In the case where it is not possible to define an AE as treatment emergent or not, the AE will be classified by the worst case (i.e. treatment emergent).

An overall summary of the number and percentage of subjects as well as the number of events within each of the categories below will be provided:

- TEAEs
- TEAEs by maximum severity
- TEAEs by highest relationship to study treatment
- TEAEs by highest relationship to study procedure
- Serious TEAE
- Serious TEAEs by maximum severity
- Serious TEAEs by highest relationship to study treatment
- Serious TEAEs by highest relationship to study procedure
- TEAE leading to treatment discontinuation
- TEAE leading to study discontinuation
- TEAE leading to death
- Post-treatment AEs
- Post-treatment AEs by maximum severity
- Post-treatment SAEs
- Post-treatment SAEs by maximum severity
- Post-treatment SAEs leading to study discontinuation
- Post-treatment SAEs leading to death.

Listings will include all AEs regardless of whether they are treatment emergent.

16.1.1. ALL TEAEs AND POST-TREATMENT AEs

Incidence of TEAEs and post-treatment AEs will be presented by System Organ Class (SOC) and Preferred Term

(PT). If a subject reports a TEAE or post-treatment AE more than once within that SOC/PT, the subject will be counted only once for that SOC/PT.

In the summary tables, TEAEs and post-treatment AEs will be presented by decreasing frequency of total events overall within each SOC and then similarly by decreasing frequency of total events overall within each PT. System organ class or PTs with equal frequencies will be sorted alphabetically.

Summaries will present TEAEs and post-treatment AEs broken down further by maximum severity. Summaries will also present TEAEs by relationship to study treatment and relationship to study procedure.

16.1.1.1. Severity

Severity is classified as mild, moderate or severe (increasing severity). TEAEs starting on or after the bilateral insertion/Sham procedure, and post-treatment AEs starting 28 days after removal procedure with a missing severity will be classified as severe for analysis purposes. If a subject reports an AE more than once within that SOC/PT, the AE with the worst-case severity will be used in the corresponding severity summaries.

16.1.1.2. TEAE Relationship to Study Treatment

Relationship, as indicated by the Investigator, is classified as “Not Related”, “Possible Related” or “Definitely Related” (increasing severity of relationship). A “related” TEAE is defined as a TEAE with a relationship to study treatment as “Possibly Related” or “Definitely Related”. TEAEs starting on or after the bilateral insertion/Sham procedure with a missing relationship to study treatment will be regarded as “Related”. If a subject reports the same AE more than once within that SOC/PT, the AE with the worst-case relationship to study treatment will be used in the corresponding relationship summaries.

16.1.1.3. TEAE Relationship to Study Procedure

The same conventions as noted in Section 16.1.1.2 will be applied to the relationship to study procedure for Day 1 insertion procedure and Week 24 removal procedure as indicated by the investigator. A TEAE related to the insertion/removal procedure is an AE that occurred within one day after the insertion/removal procedure.

16.1.2. SERIOUS ADVERSE EVENTS

Serious adverse events (SAEs) are those events recorded as “Serious” on the Adverse Events eCRF. A summary of serious TEAEs and post-treatment SAEs by SOC and PT will be prepared, including events leading to death. If a subject reports a serious TEAE/post-treatment SAE more than once within that SOC/PT, the subject will be counted only once for that SOC/PT.

Additionally, a listing of all SAEs will be provided, including events leading to death.

16.1.3. TEAEs LEADING TO DISCONTINUATION OF STUDY TREATMENT

TEAEs leading to early discontinuation of study treatment will be identified as an AE for which the “Action taken” is reported as “Study treatment discontinuation” on the Adverse Event eCRF. A summary of TEAEs leading to early discontinuation of study treatment by SOC and PT will be prepared.

Additionally, a listing of all TEAEs leading to permanent discontinuation of study treatment will be provided.

